10.1. Sample size

This study is a single-arm study, with the primary efficacy endpoint being ORR. It is planned to enroll 30 patients.

10.2. Statistical analysis plan

The detailed methods for summarization and statistical analysis of the data collected in this study will be included in the Statistical Analysis Plan (SAP), which will be finalized and filed by the sponsor. Any changes to this study protocol, if deemed by the sponsor or principal investigator to have a significant impact on the SAP, the SAP will be revised to maintain consistency with the study protocol. The SAP may revise relevant content in this protocol, but if the revision involves major and/or key factors

such as the definition of endpoints or their analyses, the revision should also be reflected in the amended version of the protocol.

10.3. Analysis populations

Full Analysis Set: includes all patients who are enrolled and receive at least one dose of study drug, and have at least one efficacy evaluation.

Safety Analysis Set: all enrolled patients who have received at least one dose of study drug and have safety records after drug administration. This dataset is used for safety analysis in the study.

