3.1. Overall design

As a single-arm, open-label, and single-center clinical study, this study aims to observe and evaluate the efficacy and safety of anti-PD-1 antibody SHR-1210 in combination with apatinib mesylate in patients with advanced mucosal melanoma. The study subjects will be the patients with advanced mucosal melanoma who cannot be cured. The study will enroll approximately 30 patients with advanced mucosal melanoma using ORR as the primary efficacy endpoint. After obtaining informed

consent and signing the informed consent form (ICF), the eligible subjects will continuously receive apatinib 500 mg, orally, once daily, and SHR-1210 200 mg, intravenously (IV), every 2 weeks (q2W). The dose of apatinib will be adjusted according to the patient's tolerance, with a treatment cycle of 4 weeks, until the treatment discontinuation events specified in the protocol occur. After the end of treatment, subjects will undergo post-treatment safety visits and survival follow-up. For subjects who discontinue treatment due to reasons other than disease progression or death, tumor progression follow-up will also be conducted after the end of treatment.

After the subjects are enrolled in the study, safety visits will be conducted before the administration of SHR-1210 on Day 1 and Day 15 of each treatment cycle. Imaging examinations will be performed every 2 cycles during the first 12 treatment cycles to evaluate the efficacy, and every 3 cycles thereafter until the end of treatment, withdrawal of informed consent, or death.

The study will also explore predictive, prognostic, and pharmacodynamic exploratory biomarkers in archived and/or fresh tumor tissue and blood samples, and assess the correlation between these biomarkers and disease progression. For subjects who have signed the ICF for biomarker sample collection, biomarker blood samples and tumor samples will be collected at baseline and during the study, including any potential tumor biopsies performed at baseline.

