6.3. End of treatment / withdrawal

If a patient experiences an event that meets the criteria in "4.3.1 Discontinuation Criteria", the patient's treatment will be terminated. At the end of the study treatment or withdrawal from the study, if the patient has not been examined within 14 days prior to the end of the study, the following tests should be conducted:

[Hematology] [Blood Chemistry] [Urinalysis] [Stool Routine] [Coagulation Function]
[Pregnancy Test] [Thyroid Function Test] [Myocardial Zymogram] [Vital Signs]

[Physical Examination] [ECOG Score] [Electrocardiogram] [Blood Pressure Monitoring] [Adverse Events] [Concomitant Medications] [Recovery of Apatinib]

If no imaging examination has been performed within 4 weeks prior to the end of treatment, an imaging examination should be conducted at the end of the study treatment or upon withdrawal from the study for efficacy evaluation. For patients with non-imaging evidence of progression (intolerable, other circumstances), tumor assessments should be performed every 3 months until disease progression, death, or initiation of other anti-tumor treatments.

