7.1. Efficacy evaluation

7.1.1. Efficacy endpoints

The primary efficacy endpoint of this study is the ORR assessed based on RECIST 1.1 criteria.

ORR: It refers to the proportion of subjects who complete at least one efficacy evaluation after treatment and have a best overall response (BOR) of CR or PR according to RECIST 1.1 criteria. If first CR or PR is achieved, the response should be confirmed no less than 4 weeks \pm 7 days after the first evaluation.

BOR refers to the best response recorded during the period from the date of initiation of treatment to the date of recorded objective progression according to RECIST 1.1 criteria or the date of initiation of new anti-tumor treatment (whichever occurs first).

For subjects who have not shown documented progression and have not initiated new anti-tumor therapy, the BOR will be determined based on all efficacy assessment results.

For subjects who continue to receive SHR-1210 after progression, the BOR should be determined based on the efficacy evaluation results recorded up to the initial occurrence of progression as defined by RECIST 1.1.

Secondary efficacy endpoints included:

- The ORR assessed by the investigator based on RECIST 1.1 criteria;
- PFS: It is defined as the time from the date of the first administration of the investigational drug to the date of the first documented tumor progression (assessed according to RECIST 1.1 criteria, regardless of whether the treatment is continued) or the date of death due to any cause (whichever occurs first).

In determining PFS, clinical deterioration occurring in the absence of definitive evidence of disease progression (according to RECIST 1.1) is not considered as disease progression. For subjects who have not previously reported progression before death, the death date will be considered as the date of disease progression. Subjects

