with neither disease progression nor death will be censored on the date of their last evaluable tumor assessment. Subjects with no tumor assessments during the study and no death will be censored on the date of first treatment. Subjects who discontinue the study due to reasons other than disease progression (without subsequent radiological examination) will be censored at the time of study discontinuation. Subjects who have not previously reported disease progression but initiate subsequent anti-tumor therapy will be censored on the date of the last evaluable tumor assessment before starting subsequent anti-tumor therapy or at the time of initiating subsequent anti-tumor therapy. When subjects are not censored at the time of study discontinuation or the time of initiating subsequent anti-tumor therapy, the prescheduled sensitivity statistical analysis will only further confirm PFS based on the time of radiologically confirmed progression event. The occurrence of new tumors is not considered a disease progression event and is not used for data censoring.

- TTR: It is defined as the time from the date of first administration to the date of the first recorded tumor response (assessed according to RECIST 1.1 criteria).
- DoR: It is defined as the time from the date of first recorded tumor response (assessed according to RECIST 1.1 criteria) to the date of first recorded tumor objective progression (assessed according to RECIST 1.1 criteria) or the date of death due to any cause. Subjects with neither disease progression nor death will be censored on the date of their last tumor assessment. Subjects who start receiving any subsequent anti-tumor treatment (excluding treatment for non-target bone lesions or palliative radiotherapy during the study treatment) and have not previously reported progression will be censored at the time of their last tumor assessment prior to starting subsequent anti-tumor treatment, or on the day of starting subsequent anti-tumor therapy.

- 6-month survival rate: It is defined as the proportion of patients with a survival duration of ≥ 6 months from the date of initial treatment;
- 9-month survival rate: It is defined as the proportion of patients with a survival duration of ≥ 9 months from the date of initial treatment;
- 12-month survival rate: It is defined as the proportion of patients with a survival duration of ≥ 12 months from the date of initial treatment;

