10.5.3. Analysis of efficacy endpoints

The point estimates will be performed for efficacy endpoints such as ORR and DCR, and their 95% CIs will be provided. The interval estimates will be performed using the Clopper-Pearson method.

PFS, DOR, OS, 6-month, 9-month and 12-month survival rates will be estimated using the Kaplan-Meier method, and 95% CIs will be calculated. TTR will be

described using mean, standard deviation, median, maximum, and minimum values.

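### The primary ORR and the Full Analysis Set leave out treated patients with no efficacy evaluation instead of counting them as non-responders, which can only raise the ORR

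*Protocol*

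**What the plan says.** Protocol section 10.3 defines two populations. The Full Analysis Set "includes all patients who are enrolled and receive at least one dose of study drug, and have at least one efficacy evaluation". The other is the Safety Analysis Set, and it is the only one that the section ties to a particular analysis.

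Section 7.1.1 defines the primary endpoint, ORR, as "the proportion of subjects who complete at least one efficacy evaluation after treatment and have a best overall response (BOR) of CR or PR". The condition of an evaluation after treatment is thus part of the endpoint itself. Section 10.5.3 asks for point estimates and 95% confidence intervals for ORR and DCR; on the intervals it says: "The interval estimates will be performed using the Clopper-Pearson method". It names no population.

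For PFS, section 7.1.1 says: "Subjects with no tumor assessments during the study and no death will be censored on the date of first treatment". It also counts death without earlier progression as an event. OS runs from first dose to death, with no evaluability condition.

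On timing, section 3.1 says "Imaging examinations will be performed every 2 cycles during the first 12 treatment cycles to evaluate the efficacy", "with a treatment cycle of 4 weeks". On patients who stop, section 6.3 says: "If no imaging examination has been performed within 4 weeks prior to the end of treatment, an imaging examination should be conducted".

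**The concern.** Inclusion in the primary analysis depends on something that happens after the first dose. The first scheduled scan comes about two months into treatment. Patients who never reach a post-treatment scan are likely to include those who did worst, and none of them can have a confirmed response. An analysis of everyone treated would count them as failures. Here they disappear from the numerator's complement, so the ORR describes patients who lasted long enough to be scanned.

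The trial has one arm, so no comparator carries the same distortion. ORR is the primary endpoint, and readers will set it beside rates from other studies whose denominators may include all treated patients.

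The population definition also sits badly with the PFS censoring text. That text provides for patients with no tumor assessment, whom the Full Analysis Set does not admit.

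**Working it through.** **Inputs from the protocol**
- Planned size (10.1): "It is planned to enroll 30 patients". No null rate, target rate, power or precision is given, so there is no design figure to reproduce. The check does not need one.
- First scheduled scan: 2 cycles x 4 weeks = week 8 (3.1), with a window of 7 days either side (6.2).
- Interval method: exact Clopper-Pearson, 95% (10.5.3).

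**Inputs assumed, because the protocol gives none**
- Responders x: 6, 9 or 12 of 30 treated (20%, 30%, 40%).
- Treated patients with no post-treatment evaluation k: 1 to 6 of 30 (3% to 20%).

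**Size of the shift.** An unevaluated patient cannot be a responder, so x is unchanged and only the denominator moves:

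ORR over all treated = x/30; ORR under the protocol's rule = x/(30-k); ratio = 30/(30-k).

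The ratio is 30/29 = 1.03 for k = 1, 30/28 = 1.07 for k = 2, 30/27 = 1.11 for k = 3, 30/26 = 1.15 for k = 4 and 30/24 = 1.25 for k = 6.

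| Responders | k = 0 | k = 2 | k = 4 | k = 6 |
|---|---|---|---|---|
| 6 | 20.0% (7.7-38.6) | 21.4% (8.3-41.0) | 23.1% (9.0-43.6) | 25.0% (9.8-46.7) |
| 9 | 30.0% (14.7-49.4) | 32.1% (15.9-52.4) | 34.6% (17.2-55.7) | 37.5% (18.8-59.4) |
| 12 | 40.0% (22.7-59.4) | 42.9% (24.5-62.8) | 46.2% (26.6-66.6) | 50.0% (29.1-70.9) |

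**Effect on the interval.** Let the number evaluable be Binomial(30, 1-q), where q is the chance of having no evaluation. Evaluable patients then respond at rate p/(1-q), where p is the true ORR among all treated. Exact enumeration gives:

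| True ORR p | q | Coverage of p by the 95% CI | Lower limit lies above p |
|---|---|---|---|
| 30% | 0 | 97.4% | 1.7% |
| 30% | 10% | 95.7% | 3.7% |
| 30% | 20% | 91.4% | 8.5% |
| 40% | 0 | 96.2% | 2.1% |
| 40% | 10% | 94.4% | 5.1% |
| 40% | 20% | 86.8% | 13.1% |

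At small q the conservatism of the exact interval absorbs much of the shift. At larger q it does not.

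**Conditional effects.** If DCR uses the Full Analysis Set, 21/30 = 70.0% becomes 21/27 = 77.8% with 3 excluded. If survival is analysed there, follow-up is complete and the excluded patients are early deaths, then 24/30 = 80.0% alive at a landmark becomes 24/28 = 85.7% with 2 excluded. If the time-to-event rules in 7.1.1 are applied to all treated patients, this source of bias is zero. A living patient censored at day 0 contributes nothing to a Kaplan-Meier curve, so only excluded early deaths could matter.

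**The two passages side by side.** Section 10.3 admits only patients with an efficacy evaluation. Section 7.1.1 gives a PFS censoring date to patients with no tumor assessment who have not died. Within the Full Analysis Set, that rule applies to nobody.

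**The case against.** Several points on the other side have force.

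- **PFS and OS.** A reader might infer that PFS, OS and the survival rates are biased upward as the protocol stands. The documents do not support that. Neither 10.3 nor 10.5.3 assigns the Full Analysis Set to these endpoints, and the rules in 7.1.1 point towards all treated patients. This stands, so the effect on these endpoints is conditional.
- **Deaths without progression.** It is also tempting to say that such patients can never be in the Full Analysis Set. That is wrong: a patient scanned as stable at week 8 who later dies without progression is in the set and counts as a PFS event. Only deaths before any evaluation are at issue.
- **Toxicity stops.** A reader might conclude that patients who stop for toxicity drop out as a class. They do not. Section 6.3 asks for a scan at the end of treatment unless one was done in the previous 4 weeks. It then asks for assessments every 3 months in patients who stop without imaging progression, and sections 4.3.2 and 7.1.2 agree. The waiver lets a baseline scan stand in only for very early stops, and those patients are still due later scans.
- **DCR.** Section 7.1.1 gives no definition of DCR, so its denominator is not known.
- **Size.** Eligibility requires ECOG 0-1 and an expected survival of at least 12 weeks, so deaths before week 8 may be few. With 12 responders and 1 or 2 exclusions, the shift is 1.4 or 2.9 points against an interval 59.4 - 22.7 = 36.7 points wide. No decision threshold is stated that could be crossed.
- **Reading of the ORR sentence.** It could be taken to describe the numerator only. Then the Full Analysis Set, as the only non-safety population, would still remove the same patients if used as the denominator.

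Leaving the matter to the SAP is not a full answer. Section 10.2 says that SAP revisions to endpoint definitions or their analyses should also appear in an amended protocol.

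**Conclusion.** The point holds for the primary endpoint. Treated patients who die, become too ill to scan, refuse imaging or start new therapy before any post-treatment scan leave the ORR denominator when they should count as non-responders. The direction is certain: the ORR rises, or stays the same if nobody is excluded. The size depends on an unknown k. For 1 to 6 exclusions, the shift is 1.0 to 7.5 points with 9 responders and 1.4 to 10.0 points with 12; both the responder counts and k are assumptions.

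For DCR, PFS, OS and the survival rates, the protocol leaves the population unstated. They are affected only if the Full Analysis Set is used and, for the time-to-event endpoints, only through early deaths that it excludes. What can be said without condition is that 10.3 and the PFS censoring rule in 7.1.1 do not fit together and need to be reconciled.

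**What to change.** - In section 10.3, define the Full Analysis Set as all patients who receive at least one dose of study drug.
- In section 7.1.1, define ORR as the proportion of all treated patients with a best overall response of CR or PR, counting those with no evaluable post-baseline assessment as non-responders. Define DCR over the same denominator, with such patients counted as not having disease control.
- State that PFS, OS and the 6-, 9- and 12-month survival rates use the same all-treated set. The PFS censoring rule for patients without tumor assessments then has patients to apply to.
- Keep the present set under a name such as response-evaluable set, as a sensitivity analysis, and report how many treated patients it leaves out and why.

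The cost is a few sentences in an amendment, with no extra patients, visits or procedures. The reported ORR may be slightly lower than under the present rule.

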10.5. Statistical methods

10.5.1. Basic methods

The main results of this study will be presented using descriptive statistical methods. The mean, standard deviation, median, maximum, and minimum values will be listed for measurement data, while the frequency (proportion), rate, and CI will be listed for counting data and ranking data. All statistical analyses will be programmed and calculated using SAS 9.4 or above.

10.5.2. Baseline characteristics

The mean, standard deviation, median, maximum, and minimum values will be calculated for measurement data such as age, height, and weight. The frequency and percentage will be listed for qualitative data such as gender and ECOG score.

10.5.3. Analysis of efficacy endpoints

The point estimates will be performed for efficacy endpoints such as ORR and DCR, and their 95% CIs will be provided. The interval estimates will be performed using the Clopper-Pearson method.

PFS, DOR, OS, 6-month, 9-month and 12-month survival rates will be estimated using the Kaplan-Meier method, and 95% CIs will be calculated. TTR will be

described using mean, standard deviation, median, maximum, and minimum values.

10.5.4. Safety analysis

The descriptive statistical analysis will be used for analyzing AEs, SAEs with \geq CTCAE grade 3, and adverse reactions (adverse reactions are defined as AEs with the causality to the study drug as "definitely related/possibly related/not evaluable"), adverse reactions with \geq CTCAE grade 3, AEs leading to dose modifications occurring in population in each dose group. The worst clinical grade will be described for the laboratory test results at baseline and post-baseline.

Additionally, the summary analysis of AEs mentioned above is also applicable for each category of immune-related AEs, including immune-related pneumonia, immune-related enteritis, immune-related thyroid dysfunction, immune-related nephritis and renal failure, immune-related hypophysitis, and other immune-related adverse reactions.

10.5.5. Exploratory analyses

For the SHR-1210-related tumor markers, such as PD-L1 in tumor tissues and TMB in tumors and plasma, descriptive statistics will be used for analysis.

11. Ethics of Clinical Studies

The clinical study will follow the relevant regulations of the World Medical Association's Declaration of Helsinki and other related provisions. The clinical study will be conducted only after the study protocol has been approved by the Ethics Committee. Before each subject is enrolled in the study, the investigator has the responsibility to provide the subject or his/her representative with a complete and comprehensive introduction of the objectives, procedures, and potential risks of the study, and to sign a written ICF. Subjects should be informed that they have the right to withdraw from the study at any time, and the ICF should be retained as a clinical

study file for future reference. The privacy and data confidentiality of the subjects will be protected throughout the study.

12. Clinical Study Schedule

Estimated first subject enrollment: January 2019

Estimated last subject enrollment: July 2021

Estimated end of study: January 2022

13. References

2. Chin L. The genetics of malignant melanoma : lessons from mouse and man. *Nat Rev Cancer* 2003(8) ; 3 : 559-570.

2013. Available from : <http://globocan.iarc.fr>, accessed on 2/10/2014.
